3.5.1.3 Adverse Events of Special Interest

The TEAEs of bleeding based on the Haemorrhages (SMQ) Export from MedDRA version 20.1 will be summarized by SOC and PT and by severity in on-treatment and on-study period.

The TEAEs of bleeding in presence or absence of concomitant anti-thrombotic medication (ATC3 Text: Antithrombotic agents) will be summarized by SOC and PT in on-treatment period. The TEAEs of bleeding in presence or absence of concomitant antithrombotic medication will be listed as well.

An additional table summarizing treatment-emergent bleeding AEs on-treatment by SOC and PT within cohort will be presented.

3.5.2 Laboratory Measurements

The following is the list of lab analytes that will be collected throughout the study:

- Chemistry: sodium, potassium, chloride, bicarbonate, total protein, albumin, calcium, magnesium, phosphorus, BUN (blood urea nitrogen), creatinine, glomerular filtration rate, uric acid, total bilirubin, direct bilirubin, indirect bilirubin, alanine aminotransferase (ALT), aspartate aminotransferase (AST), alkaline phosphatase, creatinine kinase, GGT, Cystatin-C
- Hematology: red blood cells, hemoglobin, hematocrit, MCV, MCH, MCHC, platelets, white blood cells (WBCs), and WBC differential (percentage and absolute count), neutrophils, eosinophils, basophils, lymphocytes, and monocytes
- Coagulation: aPTT, PT, and international normalized ratio (INR)
- Test Performed at Screening Only: Hepatitis B surface antigen, Hepatitis C antibody, HIV antibody, FSH (women), serum β hCG (women), TSH, T3, T4. The screening test data will only be displayed in patient listings.
- Urinalysis: color, appearance, specific gravity, pH, protein, red blood cell, glucose, ketones, urobilinogen, glucose, bilirubin, leukocytes esterase, nitrate. For expanded urinalysis at certain visits, additional measurements will be performed including: microscopic examination, P/C ratio, A/C ratio.

- 24-hour Urine Test: creatinine clearance, protein and albumin. 24-hour Urine Test will only be displayed in patient listings.
- Renal Urine Biomarkers: NGAL, NAG and KIM-1
- Other assessments (glycemic control): plasma insulin, fasting plasma glucose, homeostatic model assessment of insulin resistance (HOMA-IR) as provided in the central laboratory data, proinsulin, C-peptide, fructosamine, glycated albumin, and glycated hemoglobin (HbA1c).
- Inflammatory Panel and Liver Biomarkers (apoptosis and fibrosis): hsCRP, IL-6, IFN gamma, TNF alpha, leptin, adiponectin, CK18 and PIIINP, and if available, ceramides, sphingolipids, and diacylglycerol (to be summarized as efficacy endpoints)

Note, additional tests may be requested for specific situations. They may be summarized and will be listed per rules below too. Additional laboratory tests for patients with platelet count $<100,000/\text{mm}^3$ will be listed.

Missing WBC differential absolute counts and percentages will be derived: If WBC differential absolute counts are missing, and percentages are available, then absolute counts will be calculated by multiplying the percentage by total WBC count. Conversely, if absolute count is available, and percentage is missing, then percentage will be calculated by dividing absolute count by the total WBC count. If neutrophil counts and percentages are missing, and segmented neutrophil and band neutrophil results are available, then neutrophils will be calculated by adding segmented neutrophils and band neutrophils.

Quantitative laboratory measurements reported as '< X', i.e. below the lower limit of quantification (BLQ), or '> X', i.e. above the upper limit of quantification (ULQ), i.e. outside the limit of quantification, will be converted to X (or limit of quantification) for the purpose of quantitative summaries. If urine albumin/creatinine ratio (UACR) or urine protein/creatinine ratio (UPCR) is 'Cannot calc' indicating urine albumin or urine protein in the below quantification range, UACR and UPCR will be calculated as the ratio of urine albumin or urine protein to urine creatinine after converting urine albumin or urine protein to the limit of quantification. See Appendix C for details.

Estimated Glomerular Filtration Rate (eGFR) is based on the Chronic Kidney Disease-Epidemiological Collaboration (CKD-EPI) Equation and is provided as a parameter in the central laboratory.

All laboratory test results will be listed. Separate listings will be provided for local and central labs. A separate listing for platelets will be provided that includes assessment from both local and central labs.

Chemistry, hematology, coagulation, other assessments and quantitative urinalysis (observed value, and change and percent change from baseline) will be summarized using descriptive statistics (n, mean, standard error, standard deviation, median, 25th percentile, 75th percentile, minimum, and maximum, mean 95% CI) by nominal study visit. Urinalysis dipstick protein will be summarized using frequency counts by nominal study visit. Lab summary table except for platelet count will be based on the scheduled visits in central lab data only with the results in original unit. Two sets of

summary tables will be provided for platelets. One is based on central lab data, the other is based on local lab data. Note baseline platelets uses both central and local in its calculation.

A confirmed laboratory value is based on consecutive lab values within 7 days (no matter central lab data or local lab data). If consecutive value is the same or worse, then the initial value is confirmed. If the consecutive value is better, then the initial value is confirmed using consecutive value category. In essence, when the consecutive value is better, the initial value is not confirmed. If there is no retest within 7 days then the initial value is presumed confirmed. If there are multiple results on the same day (no matter from the same lab vendor or different lab vendors), then the worst value will be utilized in the analysis.

The following lab results will be graded per Guidance for Industry: Toxicity Grading Scale for Healthy Adult and Adolescent Volunteers Enrolled in Preventive Vaccine Clinical Trials (Sept 2007). The incidence of shift from baseline to worst post-baseline value will be summarized for on-treatment and on-study periods. Post-baseline lab results are defined as any assessment taken after the first dose no matter central lab or local lab data. If a patient is missing a baseline value but has a post-baseline value, then the baseline assessment will be labeled as “unknown”. Likewise, if a patient has a baseline value but has no post-baseline values, then the worst value will be labeled as “unknown”.

- Hemoglobin: shift from baseline to minimum post-baseline value
- WBCs: shift from baseline to minimum post-baseline value
- Platelets: shift from baseline to minimum post-baseline value
- BUN: shift from baseline to maximum post baseline value
- Creatinine: shift from baseline to maximum post-baseline value
- eGFR: shift from baseline to minimum post-baseline value
- Proteinuria: shift from baseline to worst post-baseline value
- ALT: shift from baseline to maximum post-baseline value
- AST: shift from baseline to maximum post-baseline value
- Alkaline phosphatase: shift from baseline to maximum post-baseline value
- Total bilirubin: shift from baseline to maximum post-baseline value

eGFR by will be graded using the following criteria:

- ≥ 90 mL/min/1.73m²
- ≥ 60 mL/min/1.73m² to < 90 mL/min/1.73m²
- ≥ 30 mL/min/1.73m² to < 60 mL/min/1.73m²
- ≥ 15 mL/min/1.73m² to < 30 mL/min/1.73m²
- < 15 mL/min/1.73m²

Shift tables for eGFR, ALT, AST and total bilirubin will be provided using confirmed values as well.

The number and percent of patients who met a protocol-defined safety monitoring rule(s) and stopping rule(s) (see Protocol Section 8.6 for details) will be tabulated by treatment group. A listing

will be provided for patients who met protocol-defined safety monitoring rules and for patients who terminated treatment due to a protocol-defined stopping rule as well.

Additional investigation of hepatobiliary laboratory assessments, platelet counts and renal parameters will be performed for on-treatment and on-study periods as below.

Hepatobiliary Laboratory abnormalities: The number and percent of patients falling in each of the following category will be tabulated by treatment group:

- The higher of ALT > 3 x upper limit of normality (ULN) or ALT > 2 x baseline
- ALT/AST > 3 x ULN
- ALT/AST > 5 x ULN
- ALT/AST > 8 x ULN
- ALT > 3 x ULN - ≤ 5 x ULN
- ALT > 5 x ULN - ≤ 8 x ULN
- Total bilirubin > 2 x ULN
- ALP > 2 x ULN and (baseline ALP < 2 x ULN or baseline ALP missing)

The number and percent of patients falling in each of the following categories based on confirmed worst post-baseline assessments will be tabulated by treatment group and for pooled ISIS 703802.

- ALT/AST > 8 x ULN, which is confirmed
- ALT/AST > 5 x ULN, which is confirmed and persist for at least 2 weeks
- ALT/AST > 3 x ULN (or the greater of 2 x Baseline value or 3 x ULN if the Baseline value was > ULN), which is confirmed and either:
 - Total bilirubin > 2 x ULN, or
 - INR > 1.5, or
 - Temporal association with symptoms of fatigue, nausea, vomiting, right upper quadrant pain or tenderness (coded as abdominal pain or abdominal pain upper),, fever, rash or eosinophilia as a reported laboratory result > ULN; and where temporal will be defined as the report date of the confirmed laboratory parameter occurring within the interval of the associated adverse event start and stop dates.

For patients having confirmed 3-fold or greater elevations above the ULN for ALT or AST, a listing of all the ALT, AST, total bilirubin, INR, and alkaline phosphatase records will be provided.

Abnormalities of platelet counts: The number and percentage of patients falling in each of the following categories (using available central and local laboratory assessments) based on post-baseline assessments will be provided:

- Any 2 occurrences of platelet count < 140,000/mm³
- Any single occurrence of platelet count < 100,000/mm³
- Any 2 occurrences of platelet count < 140,000/mm³ and any single occurrence of platelet count < 100,000/mm³

The nadir platelet count will be summarized by below categories:

- Decrease \geq 30% of baseline
- Decrease \geq 50% of baseline
- 100,000/mm³ to < 140,000/mm³
- 75,000/mm³ to < 100,000/mm³
- 50,000/mm³ to < 75,000/mm³
- 25,000/mm³ to < 50,000/mm³
- 0 to < 25,000/mm³

All categories of abnormalities in platelet count will be provided using confirmed values for on-study period as well.

Abnormalities of renal function: The number and percentage of patients falling in each of the following categories based on confirmed worst post-baseline assessments will be provided:

- eGFR by CKD-EPI > 25% decrease from baseline
- eGFR (CKD-EPI) value < 45 mL/min/1.73 m²
- urine albumin/creatinine ratio (UACR) > 165 mg/g (0.165 mg/mg)
- urine protein/creatinine ratio (UPCR) > 325 mg/g
- New onset hematuria defined as \geq 5 RBC/hpf (except for menstruating females)

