## 5.2 Exclusion Criteria

1. Type 1 diabetes mellitus
2. Active chronic liver disease, alcoholic liver disease, Wilson's disease hemochromatosis, primary biliary cirrhosis, primary sclerosing cholangitis, genetic hemochromatosis, known or suspected hepatocellular carcinoma, history of or planned liver transplant for end-stage liver disease of any etiology
3. Documented history of advanced liver fibrosis
4. History of cirrhosis and/or hepatic decompensation including ascites, hepatic encephalopathy, or variceal bleeding
5. Uncontrolled hypertension (systolic > 160 or diastolic > 100 mm Hg)
6. History of acute kidney injury within 12 months of Screening
7. Active infection requiring systemic antiviral or antimicrobial therapy that will not be completed prior to Study Day 1
8. Subjects with a history of major bleed or high-risk of bleeding diathesis
9. Clinically-significant abnormalities in screening laboratory values that would render a subject unsuitable for inclusion, including the following:

- a. Positive test (including trace) for blood on urinalysis. In the event of a positive test, eligibility may be confirmed with urine microscopy showing  $\leq 5$  red blood cells per high power field
  - b. Urine protein/creatinine ratio (UPCR)  $\geq 0.25$  mg/mg. In the event of a UPCR above this threshold, eligibility may be confirmed by a quantitative total urine protein measurement of  $< 300$  mg/24-hr
  - c. Estimated GFR  $< 60$  mL/min/1.73 m^2 (as determined by the Chronic Kidney Disease-Epidemiological Collaboration (CKD-EPI) Equation)
  - d. Alanine aminotransferase (ALT) or aspartate aminotransferase (AST)  $> 2$  x ULN
  - e. Bilirubin  $> ULN$ , unless prior diagnosis and documentation of Gilbert's syndrome in which case total bilirubin must be  $\leq 3$  mg/dL
  - f. Alkaline phosphatase (ALP)  $> 1.5$  x ULN
  - g. Platelet count  $< LLN$
10. Known history of or positive test for human immunodeficiency virus (HIV), hepatitis C or chronic hepatitis B
  11. Uncontrolled hyper- or hypothyroidism. Subjects on dose stable replacement therapy for at least 3 months prior to Screening will be allowed
  12. History of clinically significant acute cardiac event within 6 months before Screening (includes stroke, transient ischemic attack, and coronary heart disease [angina pectoris, myocardial infarction, revascularization procedures])
  13. History of heart failure with NYHA greater than Class II

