### 8.6.1 Stopping Rules for Liver Chemistry Elevations

In the event of confirmed laboratory results meeting any of the following criteria, dosing of a subject with Study Drug will be stopped permanently:

1. ALT or AST > 8 x ULN, which is confirmed
2. ALT or AST > 5 x ULN, which is confirmed and persists for  $\geq 2$  weeks
3. ALT or AST > 3 x ULN (or the greater of 2 x Baseline value or 3 x ULN if the Baseline value was > ULN), which is confirmed **and** total bilirubin > 2 x ULN or INR > 1.5
4. ALT or AST > 3 x ULN (or the greater of 2 x Baseline value or 3 x ULN if the Baseline value was > ULN), which is confirmed, and the new appearance (i.e., onset coincides with the changes in hepatic enzymes) of fatigue, nausea, vomiting, right upper quadrant

pain or tenderness, fever, rash, or eosinophilia ( $> \text{ULN}$ ) felt by the Investigator to be potentially related to hepatic inflammation/injury

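### The SAP 3.5.2 row combining ALT/AST above 3 x ULN with bilirubin or INR has no time link and no baseline condition for those two branches, so it can count elevations that did not occur together

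*SAP*

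**What the plan says.** SAP 3.5.2, under hepatobiliary abnormalities, has two lists. The first covers single thresholds. The second, which matters here, opens: "The number and percent of patients falling in each of the following categories based on confirmed worst post-baseline assessments will be tabulated". Its last entry takes ALT/AST above 3 x ULN, or the greater of 2 x baseline and "3 x ULN if the Baseline value was > ULN), which is confirmed and either" one of three things:

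- "Total bilirubin > 2 x ULN, or"
- INR above 1.5, or
- a temporal association with listed symptoms or eosinophilia, for which the SAP gives a date rule: "temporal will be defined as the report date of the confirmed laboratory parameter occurring within the interval of the associated adverse event start" date to its end date.

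The entry brings together two stopping criteria from Protocol 8.6.1. Criterion 3 pairs a confirmed ALT/AST elevation with "total bilirubin > 2 x ULN or INR > 1.5". Criterion 4 pairs it with new symptoms whose onset coincides with the enzyme change.

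SAP 3.5.2 runs these tables for the on-treatment and on-study periods. It also lists every ALT, AST, bilirubin, INR and ALP record for patients with confirmed ALT or AST of 3 x ULN or more.

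Protocol exclusion 9e bars bilirubin above ULN "unless prior diagnosis and documentation of Gilbert's syndrome in which case total bilirubin must be" at most 3 mg/dL.

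**The concern.** Protocol 8.5.1 says its liver alert levels exist to anticipate aminotransferases and bilirubin rising in combination. This row is where the report counts that pattern, so a reader will take it to mean that the two abnormalities were present together. The definition does not require that for bilirubin or INR. It also does not separate a bilirubin that rose on study from one that was high before dosing. Safety is part of dose selection (Protocol synopsis, Statistical Considerations), and each active arm has only 24 patients, so a single case in this row will be noticed.

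**Working it through.** The plan gives no figure for this row, so there is none to reproduce. The check compares the text of the branches and then sizes what the wording allows.

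**1. The branches side by side**

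| Component | Timing condition | Baseline condition |
|---|---|---|
| ALT/AST elevation | confirmation only | yes, if baseline is above ULN |
| Bilirubin above 2 x ULN | none | none |
| INR above 1.5 | none | none |
| Symptoms or eosinophilia | laboratory date within the adverse event's dates | new onset required in Protocol 8.6.1, not stated in the SAP |

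The SAP's 7-day confirmation rule does not fill the gap. It compares consecutive values to confirm a laboratory result and does not tie ALT/AST to bilirubin or INR. Where there is no retest within 7 days, the initial value is presumed confirmed.

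A baseline condition does appear in the first list of the same section: "ALP > 2 x ULN and (baseline ALP < 2 x ULN or baseline ALP missing"). The bilirubin line in that list has none either.

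**2. Longest gap the wording allows**

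Inputs: first 14-day chemistry sample after dosing, Day 1 + 14 = Day 15 (Protocol Appendix A); end of treatment, Day 183 (Cohort A) or Day 169 (Cohorts B and C); last follow-up target, Day 274 or Day 260 (SAP Appendix A). Visit windows are ignored.

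- Cohort A: 183 − 15 = 168 days on treatment; 274 − 15 = 259 days (37 weeks) on study.
- Cohorts B and C: 169 − 15 = 154 days on treatment; 260 − 15 = 245 days (35 weeks) on study.

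**3. Spacing of scheduled INR**

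From Day 1 on, coagulation is scheduled on Days 1, 85, 183 and 274 in Cohort A (gaps of 84, 98 and 91 days) and on Days 1, 85, 169 and 260 in Cohorts B and C (gaps of 84, 84 and 91 days). An INR close to an ALT peak therefore usually depends on the retesting in Protocol 8.5.1. That retesting is at least weekly, includes INR and bilirubin, and starts once ALT or AST above 3 x ULN is confirmed.

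**4. Bilirubin above 2 x ULN at entry**

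The ULN is an assumption, since the documents do not give it. An eligible patient with documented Gilbert's syndrome can exceed 2 x ULN when 3 > 2 x ULN, that is, when ULN is below 1.5 mg/dL.

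| Assumed ULN (mg/dL) | 2 x ULN | 3 mg/dL as a multiple of ULN |
|---|---|---|
| 1.0 | 2.0 | 3.00 |
| 1.2 | 2.4 | 2.50 |
| 1.4 | 2.8 | 2.14 |
| 1.5 | 3.0 | 2.00 (not above) |

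Bilirubin alone does not complete the row. ALT/AST must also be confirmed above the row's threshold, and exclusion 9d keeps screening values at or below 2 x ULN.

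**5. Weight of one case**

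1/24 = 4.2% of an arm; 1/72 = 1.4% of the 3 x 24 = 72 active patients.

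**6. Illustration of how much a time link would change**

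Suppose a patient has one ALT and one bilirubin elevation, independent and uniform over T days. The chance that they fall within w days of each other is 1 − (1 − w/T)². For w = 28 this gives 1 − (1 − 28/259)² = 20.5% with T = 259, and 1 − (1 − 28/168)² = 30.6% with T = 168. The present wording would count all such pairs. This says nothing about how often both elevations occur, and the documents give no rate.

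**The case against.** The case for leaving the row alone has real substance.

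- **The SAP is silent on dates and does not prescribe mismatched pairs.** A reader might infer that it instructs the programmer to pair each analyte's own peak regardless of date. It does not say so, and a programmer could pair by date. But nothing requires that, and the worst-value basis points the other way. Silence also allows the opposite error: requiring the two worst values to share a date would miss a concurrent case whose peaks differ.
- **The listing covers every affected patient.** Anyone in the row has a confirmed elevation large enough for the record-level listing, so the timing can be read patient by patient. With arms of 24, a single case would be. This stands, and it is the main reason the point is minor. The listing does not alter the number and percent in the table.
- **The row mirrors stopping criterion 3, which has neither a window nor a Gilbert's exemption.** Counting such a patient is therefore faithful to the protocol. This also stands. However, the criterion is applied during care with medical review, while a programmed count has no such judgement.
- **Over-inclusion suits a safety screen.** It fits the SAP's worst-case conventions elsewhere and applies equally to placebo. This is a good reason to keep the row.
- **A 7-day pairing window in place of the row could lose real cases.** The SAP's 7 days serve another purpose, and scheduled INRs are 12 to 14 weeks apart. This is accepted: the row should not be replaced.
- **The ALP comparison is limited.** That condition sits in the single-threshold list. It shows that the authors considered baseline for one analyte, and no more.

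**Conclusion.** The gap is real but modest. As worded, the row can include patients whose ALT/AST and bilirubin or INR elevations were up to 168 days apart on treatment, or 259 days on study. It can also include a bilirubin that was above 2 x ULN before dosing. The second route depends on a ULN below 1.5 mg/dL, which is assumed, and on a confirmed ALT/AST elevation above the row's threshold. No frequency can be put on either route from the documents.

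Two stronger readings are not supported. A reader might infer that Gilbert's bilirubin by itself, or with any rise in ALT, counts as a case; the row's ALT/AST threshold rules that out. A reader might also infer that the report would mislead on the liver safety of a dose; the full listing makes that unlikely, and the SAP labels these entries laboratory abnormalities, not liver injury. The primary analysis is untouched. The change is worth considering, not essential.

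**What to change.** Change SAP 3.5.2 only, leaving the stopping rule as it is:

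1. Keep the existing row and label it as an inclusive screen without a timing requirement.
2. Add beside it a count in which the bilirubin or INR value falls within the same ALT/AST elevation episode. One possible definition runs from the first value above the row's threshold until ALT and AST are both back to 2 x ULN or below, which matches the end of retesting in Protocol 8.5.1. The sponsor may justify another, but it should be fixed before unblinding.
3. Report the bilirubin, INR and symptom branches on separate lines, so that time-linked symptom cases are not mixed with unlinked laboratory pairs.
4. Show patients with documented Gilbert's syndrome or baseline bilirubin above 2 x ULN on their own line.

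The cost is a few table lines and one date condition in the program. The samples are already scheduled. No case is lost: a bilirubin or INR elevation just outside the episode still appears in the inclusive row and the listing.

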All lab samples are to be sent to the central laboratory by overnight courier and processed. Lab Alerts issued as per protocol safety monitoring requirements or stopping rules will indicate the applicable protocol section to facilitate review and will be immediately and simultaneously sent by email to the Investigator, the Sponsor and the CRO Medical Monitors, the Sponsor Drug Safety Physician, and the Clinical Trial Manager (CTM), and should be received by them within 2 days from sample collection. Hematology results from the site's local laboratories are received by the Study Center staff per the local laboratories' standard reporting time and should be entered as soon as possible into the eCRF to inform the Sponsor and CRO study monitoring teams.

All platelet count results must be reviewed promptly (within 48 hours of receipt) by the Investigator, or designee, to ensure that the count has not met the stopping rule and to determine whether the rate of decline is suggestive that the subject could be approaching the dose interruption rule of 75,000/mm^3 as specified in [Section 8.6.3](#). Any case of a platelet count reduction to levels below 50,000/mm^3 is considered an adverse event of special interest and must be reported in an expedited fashion to the Sponsor as per [Sections 9.3.3](#) and [9.4.1](#).

All liver and renal function tests must also be reviewed promptly (within 48 hours of receipt) by the Investigator, or designee, to ensure that the result has not met the stopping rule. Any event meeting renal stopping rules criteria described in [Section 8.6.2](#) is considered an adverse event of special interest and must be reported in an expedited fashion to the Sponsor as per [Sections 9.3.3](#) and [9.4.1](#).

All lab alerts received, including those related to platelet, liver, or renal function monitoring/stopping rules, are also reviewed promptly by the Sponsor and the CRO Medical Monitors who will agree on actions to be taken. Within 24 hours of receiving an actionable lab alert the CRO Medical Monitor will communicate instructions to the Investigator and the study

personnel by emailing them the Safety Surveillance Form that needs to be signed by the Investigator/study personnel and promptly returned to the Sponsor and CRO Medical Monitor. In urgent cases, such as platelet results below 50,000/mm^3, or liver or renal test results reaching a critical stopping rule the Investigator must also be contacted by phone.

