## 8.5 Safety Monitoring Rules

Please refer also to the “Guidance for Investigator” section of the Investigator’s Brochure.

For the purposes of safety monitoring, Baseline is defined as the average of the pre-dose test closest to Day 1 and the Day 1 value itself.

In addition to the standard monitoring of clinical safety parameters, the following guidelines are provided for the monitoring of selected parameters chosen based on preclinical and clinical observations.

In case of discrepancy between the test results from 2 sources, such as between the central and local lab, safety-mandated action must be initiated based on the more critical (lower or higher, as relevant) of the 2 values.

**Confirmation Guidance:** At any time during the study (treatment or post-treatment follow-up periods), the clinical laboratory results meeting any of the safety monitoring criteria presented below **must be confirmed** by performing measurements (ideally in the same laboratory that performed the initial measurement) on new specimens prior to administering the next dose of Study Drug (ISIS 703802 or placebo). All new specimen collections should take place as soon as possible (ideally within 3 days of the initial collection).

In addition, as described in [Section 6.2](#) hematology labs should be sent in parallel to the central and local laboratory for analysis.

**Stopping Rule Guidance:** The Investigator may interrupt or permanently discontinue study treatment for any medical reason including changes in clinical laboratory results.

In the event of an initial clinical laboratory result that meets a stopping criterion, subjects must not be re-dosed until a confirmatory test result has been reviewed by the Study Medical Monitor. If any of the stopping criteria described below are met and are confirmed, the subject will be permanently discontinued from further treatment with Study Drug (ISIS 703802 or placebo), evaluated fully as outlined below and in consultation with the Study Medical Monitor or appropriately qualified designee, and will be entered into the post-treatment evaluation portion of the study. In general, subjects who do not meet the stopping rules based upon retest may continue dosing. However, the Investigator and the Study Medical Monitor (or appropriately qualified designee) should confer as to whether additional close monitoring of the subject is appropriate.

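### The SAP's symptomatic liver row tests whether a symptom is ongoing on a lab report date, while the protocol criterion it mirrors asks for onset that coincides with the enzyme change

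*SAP*

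**What the plan says.** Protocol 8.6.1, criterion 4, combines a confirmed ALT or AST above 3 x ULN (or the baseline-adjusted limit) with "the new appearance (i.e., onset coincides with the changes in hepatic enzymes) of fatigue, nausea, vomiting" or other listed signs, "felt by the Investigator to be potentially related to hepatic inflammation/injury". It therefore has a timing condition and a relatedness condition.

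SAP 3.5.2 has a block of hepatobiliary rows that follows 8.6.1: above 8 x ULN; above 5 x ULN for at least 2 weeks; and above 3 x ULN with raised bilirubin, raised INR or symptoms. The enzyme limits are the same and the symptom list is nearly so. The timing condition differs: the symptom must be temporally associated, defined by the "report date of the confirmed laboratory parameter occurring within the interval of the associated adverse event start and stop dates". The list also includes "eosinophilia as a reported laboratory result > ULN". The row sets no limit on how early the adverse event may have started, does not require it to be treatment-emergent, and has no relatedness condition.

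On confirmation the SAP says: "A confirmed laboratory value is based on consecutive lab values within 7 days". If there is no retest in that time, the initial value is presumed confirmed.

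Earlier in the same section, the SAP separately tabulates patients who met a Protocol 8.6 rule and lists those whose treatment ended because of one. The hepatobiliary rows follow as additional investigation.

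**The concern.** The protocol asks when the symptom began. The SAP row asks whether the symptom's interval covers a reporting date. These are different questions, and the answers can differ in both directions.

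A report date is also an administrative date. It falls after the sample was drawn, and the sample may itself fall well after the enzymes rose. The term is undefined: it could belong to the initial or the repeat sample. Because the rows are based on the worst confirmed post-baseline value, it could even belong to a sample later than the first crossing of 3 x ULN.

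What is at stake is a safety table. A reader will take this row as the count of symptomatic liver cases under 8.6.1, and it may not be. Liver enzyme elevation is a risk the protocol itself names (Section 2.5.2). With about 24 patients per group, one patient is 1/24 = 4.2 percentage points, as in every row of these tables.

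**Working it through.** The plan states no figure to reproduce. The check applies both rules to the same timelines, then finds the shortest symptom the SAP row can count.

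**Inputs**
- Lag from sample to report, L: 0 to 2 days. Protocol 6.2 says that lab alerts "should be received by them within 2 days from sample collection"; alert receipt stands in for the undefined report date.
- Time from first raised sample to retest, c: 3 days (Protocol 8.5, "ideally within 3 days of the initial collection") or 7 days (the SAP confirmation window). c = 0 means the initial sample's report is used.
- Liver sampling: every 14 days for 3 months, then monthly (Protocol 8.5.1). A month is taken as 28 days.
- Assumption: onset within 7 days of the rise counts as coincident. The protocol gives no window.
- Assumption: an ongoing adverse event has an open stop date. The SAP imputes stop dates only for resolved events with partial dates.

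**Rules**
- SAP row: start ≤ report date ≤ stop.
- Protocol timing: start close to the enzyme rise.

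**Timelines, enzyme rise on day 100**

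| Symptom | Report day | Onset coincides? | SAP row counts it? |
|---|---|---|---|
| Vomiting, days 100–101; sample day 100 | 102 (100 + 2), or 105 (retest 103 + 2) | Yes | No |
| Symptom, days 100–106; sample day 107 | 109 (107 + 2) | Yes | No |
| Symptom starting day 105, 3 days after the report | 102 | Yes | No |
| Fatigue from day 10, ongoing | 105 | No | Yes |
| Symptom, days 100–120 | 105 | Yes | Yes |

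**Shortest symptom counted.** Let onset fall on the day of the rise and the first raised sample g days later. The report day is g + c + L after onset. A symptom of D days covers days 0 to D − 1, so it is counted only if D ≥ g + c + L + 1. With L = 2:

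| Report used | g = 0 | g = 13 (rise just after a 2-weekly sample) | g = 27 (rise just after a monthly sample) |
|---|---|---|---|
| Initial sample (c = 0) | 3 days | 16 days | 30 days |
| Retest on day 3 (c = 3) | 6 days | 19 days | 33 days |
| Retest on day 7 (c = 7) | 10 days | 23 days | 37 days |

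The last two columns assume that the symptom did not itself trigger a liver test.

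**The undefined term alone can change the answer.** Take nausea on Days 60–62 with the first raised sample on Day 61. The initial report falls on Day 61, 62 or 63 (61 + 0, 1 or 2); the first two count the patient and the third does not. The retest report falls on Day 66 (61 + 3 + 2) and does not count the patient.

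**Eosinophilia.** It enters as a laboratory value, so it has no adverse event start and stop dates, and the interval test cannot be carried out.

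**The case against.** The strongest reply is that the SAP already counts patients meeting the Section 8.6 rules in a separate table, lists those stopped, and presents these rows as additional. That stands, and it limits the harm. It does not remove the problem: the separate table has no derivation for the symptomatic criterion and is not said to be split by criterion, so the two outputs may disagree with no means of seeing why.

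Second, other provisions narrow both errors. Protocol 8.5.1 calls for prompt liver tests when hepatic symptoms appear, which shortens the gap from onset to sample. Protocol 9.4 sends conditions present before consent to medical history unless they worsen, so false counts need an event that started or worsened after consent. Neither provision closes the gap.

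Third, the SAP lists liver records for patients with confirmed 3-fold elevations, and lists all eCRF data. A careful reader can check individual patients. That is true, but it is not a reason to leave the summary row wrong.

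A reader might also want a miss rate. If onset is taken as uniform over the 15 days from −7 to +7 around the raised sample, a symptom of 7 days or less is counted in duration/15 of cases: 1/15, 3/15 or 7/15 for 1, 3 or 7 days. That share is the same for a report on day 0, +2 or +5. It reflects the assumed window and says nothing about the lateness of the report date. The documents give no distribution of onset or duration, so no rate is supported.

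**Conclusion.** The two passages conflict. The SAP row measures overlap with a report date, not new onset. It can include symptoms that long precede the rise and omit coincident ones, and it has no workable rule for eosinophilia. The term report date is undefined.

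The consequence is modest. It is confined to one supplementary safety row, which may differ from the separate Section 8.6 count. The minimum durations above are illustrations under the stated lags and sampling intervals, not expected frequencies.

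Three stronger readings are not supported:
- That patients would be wrongly stopped or kept on drug. Dosing follows Protocol 8.6.1, not the SAP table.
- That the row will certainly disagree with the patients actually stopped. It may; the documents do not show that it must.
- That dose selection turns on this row. The protocol synopsis names triglyceride reduction, treatment-related SAEs and other safety considerations including platelet reductions. It does not name this row.

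**What to change.** Reconcile SAP 3.5.2 with Protocol 8.6.1 by redefining the row; the clinical rule itself is not touched.

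1. Count a listed symptom if it is treatment-emergent and its start date lies between two sample dates. The lower limit is the collection date of the last ALT/AST sample below the threshold. The upper limit is a stated number of days after the collection date of the first raised sample of the confirmed elevation. Exclude events that started earlier. Using the last sample below the threshold as the lower limit keeps symptoms that began during an unsampled rise when tests are monthly; a fixed window of 7 days either side would drop some of these.
2. For eosinophilia, use the collection date of the first value above ULN as the start date.
3. State that the Investigator's view of hepatic relatedness is not part of the row unless the CRF captures it. The relationship to Study Drug recorded under Protocol 9.4.3.1 is a different question.
4. Split the existing Section 8.6 stopping-rule tabulation by criterion, so that the two counts can be compared.

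The cost is a few sentences in the SAP and a small programming change using start and collection dates. The drawback is that the length of the window after the raised sample is a convention and must be stated in advance.
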